4.5.8.3 Physical Examination

Any relevant physical examination findings at Visit 1 are included as part of the patient's medical history. Any changes seen after Visit 1 that are indicative of an AE are to be recorded as such on the AE form and included as part of the AE summaries.

Additionally, height and weight are recorded as part of the physical examination. Height and weight will be summarized and listed together with the vital signs parameters.

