- Change in growth and development for patients less than 18 years of age by measurement of height, weight, insulin-like growth factor-1 (IGF-1) levels and Tanner Staging (for patients aged 10–17 [inclusive], or earlier if clinically

indicated by onset of menarche or other signs of precocious puberty), relative to the pre-randomization baseline of the Core Study.

- Effects on menstruation cycles (in females).
- Drug abuse liability, as measured by AEs of abuse potential, drug accountability and Study Medication Use and Behavior Survey in patients aged 12 and older.

DS Patients Only:

- Percentage change in total convulsive seizure frequency, relative to the pre-randomization baseline of the Core Study.
- Percentage change in total non-convulsive seizure frequency, relative to the pre-randomization baseline of the Core Study.
- Number of patients considered treatment responders, defined as those with a $\geq 25\%$, $\geq 50\%$, $\geq 75\%$, or 100% reduction in convulsive seizures, relative to the pre-randomization baseline of the Core Study.
- Number of patients experiencing a $> 25\%$ worsening, $- 25$ to $+ 25\%$ no change, $25-50\%$ improvement, $50-75\%$ improvement or $> 75\%$ improvement in convulsive seizures, relative to the pre-randomization baseline of the Core Study.

LGS Patients Only:

- Percentage change in the number of drop seizures, relative to the pre-randomization baseline of the Core Study.
- Percentage change in the number of non-drop seizures, relative to the pre-randomization baseline of the Core Study.
- Number of patients considered treatment responders, defined as those with a $\geq 25\%$, $\geq 50\%$, $\geq 75\%$, or 100% reduction in drop seizures, relative to the pre-randomization baseline of the Core Study.
- Number of patients experiencing a $> 25\%$ worsening, $- 25$ to $+ 25\%$ no change, $25-50\%$ improvement, $50-75\%$ improvement or $> 75\%$ improvement in drop seizures, relative to the pre-randomization baseline of the Core Study.

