4.1.1.1 Choice of Baseline

For all visit-based endpoints, change from baseline will be calculated with reference to the core study baseline only.

For seizure-related endpoints, percentage change from baseline will be calculated from the core study baseline period.

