4.5.8 Vital Signs, Other Physical Findings and Other Safety Data

4.5.8.1 Vital Signs

All vital signs measurements are taken in a sitting position after five minutes of rest.

Summaries for vital signs (systolic blood pressure, diastolic blood pressure, pulse rate, temperature and respiratory rate) will be presented for each vital sign parameter at each visit. Change from baseline to each post-baseline visit will also be presented.

Based on the criteria presented in Section 6, clinically significant changes from core study baseline in vital signs measurements and other defined flagged values will be identified at each visit. The number of patients with a clinically significant change from core study baseline will be summarized by parameter and visit. The number of patients with at least one post-baseline flagged vital sign parameter value will be summarized by parameter and flagged criteria.

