4.5.8.11 Growth and Development

IGF-1 levels will be analyzed as part of the clinical laboratory testing. IGF-1 levels will be summarized on a continuous scale, including change from baseline.

The pubic hair growth (both sexes), genital (males only) and breast (females only) development of all adolescent patients (i.e., 10 to less than 18 years of age at the time of signing the informed consent form, or earlier if clinically indicated by onset of menarche or other signs of precocious puberty) will be assessed using Tanner Staging. The patients will undergo a discreet physical examination and be assigned a value under each category of pubic hair growth (both sexes), genitals (males only), and breasts (females only).

Patients will be examined at Visit 1 (Day 1) and the end of treatment visit. Once a patient reaches a score of V (i.e., 5) the examination need not be performed again.

Tanner Stages will be summarized on a categorical scale.

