7. ATTACHMENTS AND APPENDICES

Appendix 1 Adverse Events of Special Interest – Abuse Liability

Withdrawal	Drug withdrawal convulsions
	Drug withdrawal headache
	Drug withdrawal maintenance therapy
	Drug withdrawal syndrome
	Drug withdrawal syndrome neonatal
	Drug rehabilitation
	Rebound effect
	Steroid withdrawal syndrome
	Withdrawal arrhythmia
	Withdrawal syndrome
Drug abuse and dependence	Dopamine dysregulation syndrome
	Drug abuse
	Drug abuser
	Drug dependence
	Drug dependence, antepartum
	Drug dependence, postpartum
	Intentional drug misuse
	Intentional overdose
	Maternal use of illicit drugs
	Neonatal complications of substance abuse
	Polysubstance dependence
	Substance abuse
	Substance abuser
	Accidental overdose
	Dependence
	Disturbance in social behaviour
	Drug administered at inappropriate site
	Drug detoxification
	Drug diversion
	Drug level above therapeutic
	Drug level increased
	Drug screen
	Drug screen positive
	Drug tolerance
	Drug tolerance decreased
	Drug tolerance increased
	Medication overuse headache
	Narcotic bowel syndrome
	Needle track marks
	Overdose
	Prescribed overdose
	Prescription form tampering
	Substance use
	Substance-induced mood disorder
Substance-induced psychotic disorder	
Toxicity to various agents	

Appendix 2 Ranges for Clinically Significant Changes and Other Defined Flagged Values in Vital Signs

The range of values that will be used to identify clinically significant changes in vital signs parameters (See Section 4.5.8.1) are presented in Table 7.

Table 7 Ranges for Clinically Significant Changes in Vital Signs

Vital Sign	Range
Sitting Systolic BP	Change: < -20, > 20
Sitting Diastolic BP	Change: < -10, > 10
Pulse Rate	Change: < -15, > 15
Weight	Percent Change: $\leq -7, \geq 7$

Defined flagged values that will be used to identify low or high vital signs parameters (See Section 4.5.8.1) are presented in Table 8.

Table 8 Other Defined Flagged Values for Vital Signs

Vital Sign	Flag
Sitting Systolic BP	< 90, > 140, > 160
Sitting Diastolic BP	< 50, > 90, > 100
Pulse Rate	< 60, > 100
Temperature	> 38.0, < 36.0
Respiratory Rate	< 12, > 20

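### For patients under 18, the SAP summarises height and weight only as raw change and applies one ±7% weight flag at every age and follow-up time, so its tables do not describe faltering growth

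*SAP*

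**What the plan says.** The Protocol (4.1.2) lists as a secondary endpoint "Change in growth and development for patients less than 18 years of age by measurement of height, weight", together with IGF-1 and Tanner stage. Height and body weight also belong to the primary safety endpoint (Protocol 4.1.1; SAP 3.3.1). SAP 4.7 names the protocol endpoints that are dropped, and growth is not among them.

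The analysis is spread over several places in the SAP:

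- 4.5.8.3, on height and weight: "Height and weight will be summarized and listed together with the vital signs parameters".
- 4.5.8.1, on vital signs: "Change from baseline to each post-baseline visit will also be presented". For the weight limits it adds: "The number of patients with a clinically significant change from core study baseline will be summarized by parameter and visit".
- 4.1.1.1, on the reference point: "For all visit-based endpoints, change from baseline will be calculated with reference to the core study baseline only".
- Appendix 2, Table 7, headed "Ranges for Clinically Significant Changes in Vital Signs", sets the weight limit at a change of 7% or more in either direction. It varies with neither age nor follow-up time. Height does not appear.
- 4.5.8.11, the growth section, covers Tanner stage and IGF-1 and does not mention height or weight. It says: "IGF-1 levels will be summarized on a continuous scale, including change from baseline".

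Tables are split by indication (4.1). The age bands, from 2–5 to 18–55 years, appear only under demographics (4.4.4). No z-score, centile, growth velocity or growth reference is planned for any growth measure, although 4.5.6 uses age-standardised scores for Vineland-II.

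**The concern.** Raw change in height or weight in a child is driven mostly by age and by time since baseline. In a randomised comparison, normal growth would largely cancel between arms. This study has one group (Protocol 7.1), so nothing in the tables separates ordinary growth from a departure from it.

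A fixed percentage limit on weight then errs in both directions. Given time, a child growing normally crosses +7%. A child whose weight stalls shows 0% and stays inside the limits. The SAP also does not say whether losses and gains are counted separately. If they are pooled, expected gains would swamp true losses.

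At stake is whether the summary tables answer the growth objective for under-18s.

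**Working it through.** The plan gives no derivation of the 7% limit and no sample size or power, so it has no figure of its own to reproduce. The check asks what the limit does when followed as written.

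**Inputs from the documents**
- Weight limits: −7% and +7% (SAP Appendix 2, Table 7).
- Reference point: Core Study baseline (SAP 4.1.1.1).
- Core treatment period: 14 weeks, except 21 days in GWEP1332 Part A (SAP Table 1).
- OLE duration: at most 208 weeks (Protocol 4.1).

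**Assumption**
- Normal annual weight gain g of 5–12%, compounding. The documents give no growth rate. Step 1 does not need it.

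**Step 1. Growth that alone reaches +7%.** Let T = (OLE week + 14)/52.18 years. The break-even gain is 1.07^(1/T) − 1.

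| OLE week | T (years) | Annual gain reaching +7% |
|---|---|---|
| 24 | 0.73 | 9.7% |
| 48 | 1.19 | 5.9% |
| 104 | 2.26 | 3.0% |
| 208 | 4.25 | 1.6% |

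On OLE time alone, ignoring the Core period, the figures for Weeks 48, 104 and 208 are 7.6%, 3.5% and 1.7%. The weeks are from the Protocol schedule. SAP Table 2 labels scheduled visits only to Week 76 and then End of Treatment, so later growth would appear there.

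**Step 2. Early visits.** Day 85 is about 26 weeks from Core baseline (12 + 14), or 0.50 years. Expected gain is 1.05^0.50 − 1 = 2.5% to 1.12^0.50 − 1 = 5.8%. Average normal growth is still inside the limit there.

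**Step 3. A child with no weight gain.** Change is 0%, so neither limb of Table 7 is reached at any visit. The shortfall against expected weight is 1 − 1/(1+g)^t. At t = 2 years from Core baseline:
- g = 5%: 1 − 1/1.1025 = 9%.
- g = 12%: 1 − 1/1.2544 = 20%.

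**Step 4. Shortfall needed to reach −7%.** This is 1 − 0.93/(1+g)^t.
- t = 2: 1 − 0.93/1.1025 = 16% to 1 − 0.93/1.2544 = 26%.
- t = 4: 1 − 0.93/1.2155 = 23% to 1 − 0.93/1.5735 = 41%.

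**Step 5. The same child on a standardised scale.** The approximate change in weight z-score is −T × ln(1+g)/CV. Take g = 10% and, as a further assumption, a between-child weight CV of 12–18%.
- Week 48: −0.113/0.18 = −0.6 to −0.113/0.12 = −0.9.
- Week 104: −0.216/0.18 = −1.2 to −0.216/0.12 = −1.8.

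A child growing along the reference has an expected change of 0 throughout. A z-score therefore moves for the child whom Table 7 misses and stays put for the child whom it flags.

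**The case against.** Several points on the other side have force.

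- **IGF-1.** A reader might infer that IGF-1 is examined only as raw change. It is listed under biochemistry in Protocol Table 9.1.9-1, and SAP 4.5.3.1 plans shift tables against normal ranges for biochemistry. If the laboratory's ranges are specific to age and sex, IGF-1 is already partly adjusted. The documents do not say whether they are. The gap for IGF-1 is this missing statement.
- **Early visits.** A reader might infer that the weight flag fails throughout. Step 2 shows otherwise: at Day 85 average normal growth does not trip it, and the lower limb can still pick up acute loss. The failure belongs to later visits, and to weight only, since height has no flag.
- **Attribution to the drug.** It is tempting to say that the tables cannot show whether the drug impairs growth and that z-scores would. The study is descriptive and uncontrolled, so z-scores would not attribute a departure to the drug either. The defect is in describing growth.
- **Other safeguards.** Physical changes that indicate an adverse event are recorded as such (SAP 4.5.8.3), Tanner stages are tabulated (Table 14.5), and height, weight and BMI are listed by patient (Listing 14.1.3). An individual case might be noticed. These safeguards rely on someone noticing, and none summarises height or weight growth.
- **Reading of the SAP.** Section 4.5.8.1 names five vital signs without height or weight. That raw change is planned for both is read from 4.5.8.1 and 4.5.8.3 together. Table 7 confirms it for weight.
- **Duration and rates.** Four years is a maximum, and some patients finished at one year (SAP Table 2). Zero gain for years is an extreme illustration, and the growth rates are assumed. The break-even figures in Step 1 do not depend on those rates, and the problem is already present at Week 48 for gains above about 6% a year.

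**Conclusion.** The concern holds for paediatric height and weight. From about Week 48 the upper limb of the weight flag increasingly marks ordinary growth, and a child who gains nothing is never marked by Table 7. The direction rests only on the fixed limit and the Core baseline. The break-even rates assume a 14-week Core period with no gap before the OLE. The shortfalls of 9–20% (no gain, 2 years), 16–26% (lower limb, 2 years) and 23–41% (lower limb, 4 years) rest on the assumed 5–12% annual gain.

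The planned summary tables therefore do not describe growth faltering in under-18s. The documents do not support the wider inferences that faltering would necessarily go unnoticed, or that IGF-1 has no range-based analysis.

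**What to change.** In SAP 4.5.8.3, 4.5.8.11 and Appendix 2:

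- For patients under 18, summarise height, weight and BMI as age- and sex-standardised z-scores at each visit, with change from Core Study baseline, against a named growth reference.
- For this age group, replace the percentage weight flag in the tables with a fall in weight z-score. Set the threshold in the SAP before database lock, and justify it there.
- Count losses and gains separately. Keep ±7% for adults.
- State that the IGF-1 shift tables use age- and sex-specific normal ranges, or use IGF-1 z-scores if the laboratory supplies a reference.
- Correct the cross-reference in 4.5.8.1, which sends the reader to Section 6 (the references) for limits that stand in Appendix 2.

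Date of birth, sex, height, weight and IGF-1 are already collected, so the cost is SAP wording and programming. The downside is that a reference population must be chosen, and z-scores describe departure from it without saying what caused the departure.

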4.5.8.4 Columbia-Suicide Severity Rating Scale

The C-SSRS is completed for patients who are 6 years and older and capable of understanding and answering the questions, in the investigator's opinion. Questions are asked on suicidal behavior, suicidal ideation and intensity of ideation. At the screening visit, questions are in relation to lifetime experiences and all subsequent questioning in relation to the last assessment.

The following C-SSRS data will be summarized at each visit for patients in the safety analysis set:

- Incidence of the following suicidal ideation:
 - Wish to be dead.
 - Non-specific active suicidal thoughts.
 - Active suicidal ideation with any methods (not plan) without intent to act.
 - Active suicidal ideation with some intent to act, without specific plan.
 - Active suicidal ideation with specific plan and intent.
- Incidence of the following suicidal behavior:
 - Actual attempt.
 - Interrupted attempt.
 - Aborted attempt.
 - Preparatory acts or behavior.
 - Suicidal behavior.
 - Completed suicide.

In addition, the number of patients with any suicidality, any suicidal ideation and any suicidal behavior will be summarized. Suicidality is defined as at least one occurrence of suicidal behavior or suicidal ideation.

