9.1.11.5 Columbia-Suicide Severity Rating Scale (Six Years of Age and Older)

The definitions of behavioral suicidal events used in this scale are based on those used in the Columbia-Suicide History Form. Questions are asked on suicidal behavior, suicidal ideation and intensity of ideation. Questioning will be in relation to the last assessment (Since Last Visit).

The C-SSRS is to be completed by the Investigator or his/her qualified designee at every visit as indicated in the Schedule of Assessments (see [APPENDIX 1](#)); "qualified designee" is defined as anyone who has completed the C-SSRS training within the past 2 years. The survey should be completed by the same assessor, where possible, throughout the study. The Children's C-SSRS will be used for patients aged 6–18 (inclusive) while the C-SSRS will be used for patients aged 19 and older. For patients that become 6 years old during this OLE trial, the Children's Baseline C-SSRS (employing questions in relation to lifetime experience) should be completed at the next trial visit. Questioning at all subsequent visits will be in relation to the last assessment (Children's Since Last Visit).

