13.1 Sample Size, Power and Significance Levels

As this is an open label safety study, there is no formal sample size calculation. All patients who wish to continue on IMP from the populations included in the double-blind Phase 2 and Phase 3 Core Studies in DS and LGS will be eligible for inclusion. Approximately 680 patients will be enrolled.

All data collected during this study will be summarized across time, using appropriate descriptive statistical methods. There will be no formal hypothesis testing.

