13.6.2.4 Columbia-Suicide Severity Rating Scale Data

C-SSRS data will be summarized at baseline (Core Studies), screening (OLE Visit 1) and at each time point during the treatment period (including the taper period) using appropriate summary statistics. Changes from baseline (Core Studies) during and at the end of treatment will also be summarized.

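### C-SSRS incidence is tabulated by visit over unequal look-back windows, and lifetime forms of children turning 6 can enter on-treatment rows; a treatment-emergent table should replace the promised but unspecified change from Core baseline

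*SAP*

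**What the plan says.** Change in C-SSRS from the Core Study's pre-randomization baseline is one component of the primary safety endpoint (protocol synopsis and 4.1.1; SAP 3.3.1). Protocol 13.6.2.4 repeats it: "Changes from baseline (Core Studies) during and at the end of treatment will also be summarized".

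On the look-back, protocol 9.1.11.5 says of the OLE: "Questioning will be in relation to the last assessment (Since Last Visit". It makes one exception. A child who turns 6 during the OLE gets the Children's Baseline form: "employing questions in relation to lifetime experience) should be completed at the next trial visit". SAP 4.5.8.4 puts it differently: "At the screening visit, questions are in relation to lifetime experiences and all subsequent questioning in relation to the last assessment".

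On the analysis, SAP 4.5.8.4 says "The following C-SSRS data will be summarized at each visit for patients in the safety analysis set". It then lists incidence of each ideation and behavior type, plus counts of any ideation, any behavior and any suicidality. It gives no change from baseline, no rule for the age-6 lifetime form and no percentage denominator. The form is completed only by patients who are "6 years and older and capable of understanding and answering the questions".

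**The concern.** Three features make the planned C-SSRS output hard to interpret.

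- The visit rows cover different lengths of time, with no adjustment and no statement of the window. A rise or fall between rows may reflect only the visit schedule.
- A lifetime form completed at an on-treatment visit asks about the child's whole life, including time before any study drug, yet it falls into that visit's row.
- The promised change from Core baseline has no definition in the section that should define it.

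At stake is whether a reader of this single-arm study can see how many patients had new ideation or behavior after starting OLE drug. No planned C-SSRS table isolates that.

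**Working it through.** The plan has no numerical target to reproduce: "As this is an open label safety study, there is no formal sample size calculation". The checks below use the visit schedule and labelled assumptions.

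**1. Look-back windows.** Inputs: C-SSRS visits in protocol Appendix 1 and section 9.2, at Day 1, Weeks 24, 36, 48, 76, 104, 132, 156 and 184, and End of Treatment at Week 208 at the latest. Gap = week of visit minus week of previous C-SSRS visit:

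24−0 = 24; 36−24 = 12; 48−36 = 12; 76−48 = 28; 104−76 = 28; 132−104 = 28; 156−132 = 24; 184−156 = 28; 208−184 = 24 weeks.

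With ±7-day windows at both ends, a 12-week gap can be as short as 10 weeks and a 28-week gap as long as 30. End of Taper follows 10 (+3) days after End of Treatment, so its look-back is 10 to 13 days. An unscheduled End of Treatment visit makes the last gap vary by patient. SAP Table 2 labels Visit 6 as Week 38, which would turn the two 12-week gaps into 14 and 10 weeks.

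**2. Effect on visit rows.** For rare events at a constant rate, the share positive is roughly rate × window, so the ratio between rows is the ratio of windows:

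- 28 against 12 weeks: 28/12 = 2.33.
- 24 against 12 weeks: 24/12 = 2.0.
- 28 weeks (196 days) against End of Taper: 196/13 = 15.1 to 196/10 = 19.6.

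If the same patients report persistently, the ratios lie between 1 and these values.

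**3. Lifetime forms at age 6.** SAP 4.4.4 has a 2-5 year age group, so some children will turn 6 on treatment; one entering at age 4 does so within two years. Protocol 9.1.11.5 sends them a lifetime form at the next visit, and SAP 4.5.8.4 summarises every visit without excluding or flagging it. That form mixes pre-drug history with earlier time on OLE drug. The documents do not give the number of such children, so the effect cannot be sized.

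**4. Change from Core baseline.** SAP 4.1.1.1 directs that changes in visit-based endpoints use the Core baseline, and SAP 4.1.4.1 accepts whichever visit the Core Study assigned. Neither gives that form's look-back. SAP 4.5.8.2, 4.5.8.5 and 4.5.8.6 call for change explicitly; 4.5.8.4 does not. SAP 4.7 lists dropped endpoints and C-SSRS change is not among them.

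To show what a lifetime baseline would do, assume a constant hazard and no true change: share positive in a window = 1 − (1 − lifetime share)^(window/age). Lifetime shares and ages are assumptions.

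| Lifetime share | Age | 12 weeks | Apparent change (points) | 28 weeks | Apparent change (points) |
|---|---|---|---|---|---|
| 2% | 6 | 0.077% | −1.92 | 0.181% | −1.82 |
| 2% | 25 | 0.019% | −1.98 | 0.043% | −1.96 |
| 5% | 6 | 0.196% | −4.80 | 0.458% | −4.54 |
| 5% | 25 | 0.047% | −4.95 | 0.110% | −4.89 |
| 10% | 6 | 0.403% | −9.60 | 0.938% | −9.06 |
| 10% | 25 | 0.097% | −9.90 | 0.226% | −9.77 |

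Nearly the whole lifetime share would vanish through the window alone. Exclusion 6.2.4 bars any history of suicidal behavior, and ideation of type 4 or 5 at Visit 1, so this would fall mainly on ideation types 1-3.

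**5. Which visit is screening.** Protocol 13.6.2.4 uses the word for OLE Visit 1. On that reading, SAP 4.5.8.4 has lifetime questions at OLE Visit 1 while protocol 9.1.11.5 has Since Last Visit questions: a conflict. If it means Core screening, the texts agree, but whether that visit is the baseline remains open.

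**6. Denominator.** Protocol 13.1: "Approximately 680 patients will be enrolled". Suppose half are assessable (assumption) and 5% of those are positive: 680 × 0.5 = 340, and 340 × 0.05 = 17 patients. On 340 that is 5%; on 680 it is 2.5%. For assessable shares of 30%, 70% and 90%, the full-set figure is 1.5%, 3.5% and 4.5%. With assessed patients as denominator there is no dilution.

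**The case against.** The strongest reply is that this is a descriptive single-arm study with no hypothesis testing, so no inference rests on comparing visits. On-drug suicidality is also captured elsewhere: suicidality reported as an AE enters the TEAE, serious and fatal summaries (SAP 4.5.2); Listings 14.4.1 to 14.4.3 show C-SSRS ideation, behavior and attempts; and for patients aged 12 and older, suicidal thoughts or attempts trigger a Supplemental Adverse Event Form, whose completions are counted (SAP 4.6.5). The gaps are not monotone either, since the first is already 24 weeks, so the schedule does not build in a steady upward trend.

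All of this is correct, and it limits the harm. It does not supply a C-SSRS summary of new events, although the C-SSRS is named in the primary endpoint. A visit-by-visit incidence table invites comparison whether or not a test is attached.

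Two stronger readings are tempting and not supported. A reader might infer that the suicidality component is biased by a lifetime baseline; the documents do not say which form the Core baseline used, and exclusion 6.2.4 largely rules this out for behavior. A reader might also infer that unassessed patients are counted as free of suicidality; naming the safety analysis set as the population does not fix the percentage denominator, and counts are unaffected either way.

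**Conclusion.** The point holds as a weakness of method that is cheap to repair. The unequal windows follow directly from the schedule: 12 to 28 weeks at scheduled visits and 10 to 13 days at End of Taper, with a ratio of about 2.3 between the longest and shortest scheduled windows if events are rare and the rate constant. The age-6 lifetime form can place pre-drug history in an on-treatment row; its size is unknown. The mismatch between the promised change and SAP 4.5.8.4 is plain on the page.

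A spurious fall against a lifetime baseline, a conflict over the screening visit, and diluted percentages are conditional. They depend respectively on the Core baseline form, on screening meaning OLE Visit 1, and on the full safety-set N being the denominator. None of these is established.

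**What to change.** - Replace the change from Core baseline with one treatment-emergent table: patients with any ideation or behavior on a Since Last Visit form after OLE Day 1, split by whether any pre-OLE form was positive. Use patients with at least one completed post-Day-1 C-SSRS as denominator, and show person-time assessed.
- Put the lifetime forms of children turning 6 in a separate row, outside on-drug incidence. Do not discard them, because they also cover earlier OLE exposure and may hold real on-drug events.
- Keep the by-visit rows, with percentages based on patients assessed at that visit, n shown and the look-back length stated.
- State which visit SAP 4.5.8.4 means by screening, and reconcile it with protocol 9.1.11.5.
- Align the protocol synopsis, 4.1.1 and 13.6.2.4 with SAP 3.3.1 and 4.5.8.4, and record the departure in SAP 4.7.
- While there, check the titles of Tables 14.4.1 and 14.4.2: both name only the Children's form, though patients aged 19 and older use the adult one.

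The cost is wording in these sections and one extra table, with no new data collection. Reported percentages may rise if the denominator becomes smaller than the full safety set.
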